4.4 Study Drug Accountability and Compliance

Subjects will be instructed to return all used empty bottles and unused study drug at each visit.

The investigator or their appointed designee is responsible for ensuring that deliveries of study drug are correctly dispensed and recorded, that the product is handled and stored safely and properly, and that it is only being given to subjects in accordance with this protocol.

Sites will keep a current log of drug accountability recording:

- What drug supply was received from the sponsor
- What drug supply was dispensed to each subject
- What drug supply is current in inventory
- What drug supply was destroyed or returned to the sponsor for destruction

Note: Drug accountability is the responsibility of the investigator; a written account will be required for all discrepancies.

If the study drug supplies appear to be damaged/missing upon arrival at the investigational site, the sponsor should be contacted immediately.

the sponsor's designated monitor must verify all accountability records during periodic monitoring visits. Unused and used study drug must be stored on site until such accountability has taken place and authorization is received from the sponsor or sponsor's designee that the study drug may be returned or destroyed.

To stay in the study, subjects will be required to have taken at least 75% of their study treatment doses. A subject will be considered non-compliant if they have missed more than 25% of the required doses between visits. The minimum number of required doses per 7 days is detailed below:

- Week 1: 11/14 doses (22 capsules)
- Week 2: 11/14 doses (44 capsules)
- Week 3 to 4: 21/28 doses (105 capsules)

If compliance is less than 75% or greater than 125% at any visit, the reason(s) must be noted and the subject's continued participation in the study should be discussed with the study safety representative. Subjects should not make up for missed doses.

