4.8 Study Blinding

This is a double-blind study; that is, the treatment assignment and drug contents are not revealed to the sponsor, the subject and or investigator and other study personnel.

Maintenance of the double-blind is critical to the integrity of this clinical study. However, in the event of a medical emergency or pregnancy (including pregnancy in the sexual partner of a male subject) in which knowledge of the investigational product is critical to the subject's management, the blind for that subject may be broken by the treating investigator.

Before breaking the blind for an individual subject, the investigator should have determined that the information is necessary, i.e., it will alter the immediate management of the subject's care. *In the majority of cases not involving pregnancy, because there is no known specific antidote for any potential pharmacodynamic or toxic effect of CX-8998, there should rarely be a need to unblind a subject to guide immediate medical management of an emergency.*

The need to break the blind should first be discussed with the sponsor's study safety representative, if at all possible. In case of an emergency, the investigator may use the Emergency Unblinding Function under the Randomization side menu in the IWRS. Once the decision to unblind has been made, the investigator must record the nature of the emergency that required the unblinding, along with the date and time of the unblinding, in the proper source documentation and notify the sponsor's study safety representative of the unblinding. However, the sponsor's study safety representative, and any other investigators, must not be informed of the treatment assignment. The treatment assignment must not be noted in the source documentation or any other documentation submitted to the sponsor.

Study treatment for a given subject may be unblinded for reportable safety events (e.g., suspected unexpected serious adverse reaction [SUSAR]) as required by local or other regulations, but the mere occurrence of an SAE should not routinely precipitate immediate unblinding.

In cases of accidental unblinding, the investigator will notify the sponsor's study safety representative and ensure that every attempt to preserve the blind is made. Specifically, the

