investigator will not reveal the identity of the study treatment to the sponsor's study safety representative or other sponsor staff, any contract research organization (CRO) staff, including the clinical site staff, clinical research associate (CRA), subject, or anyone else who does not already know this information.

If unblinding occurs, the study drug must be discontinued for the particular subject(s) involved.

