6.4 Withdrawal of Subjects and/or Discontinuation of Treatment

A subject should be withdrawn from the study for any of the following:

- 1) Withdrawal of subject consent
- 2) Subject is lost to follow-up
- 3) Investigator determines that withdrawal from the study is in the best interest of the subject.
- 4) Subject is non-compliant with protocol-mandated activities.
- 5) Occurrence of any intercurrent condition, injury, or disease that becomes apparent during the study and necessitates the termination of the subject from the study.
- 6) Administrative reason (e.g., termination of the clinical study by a regulatory agency or the sponsor)

A subject should be discontinued from treatment for any of the following:

- 1) Subject is not at least 75% compliant with study drug administration at any study visit ([Section 4.4.](#))
- 2) Occurrence of defined unacceptable toxicity ([Section 4.5](#))
- 3) Investigator determines that discontinuation of treatment is in the best interest of the subject.
- 4) Occurrence of any intercurrent condition, injury, or disease that becomes apparent during the study and necessitates the discontinuation of treatment.
- 5) Pregnancy
- 6) Subject requires use of prohibited concurrent medication
- 7) Subjects answering "yes" to Suicidal Ideation item 4 or 5 on the C-SSRS during the study must be withdrawn from the study treatment. Investigators should also withdraw subjects from treatment if, in the judgment of the investigator, the subject develops other indicators of significant risk of suicide. In the event that suicidal ideation is observed in any study subject, the investigator will manage the situation as he/she deems medically and psychiatrically appropriate.

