5. Dose modification and stopping rules are in place for individual subjects (see [Section 4.5, Dose Adjustments/Toxicity Management](#)). Near real-time safety and tolerability monitoring for individual subjects is the primary responsibility of the PI and sub-I's.
6. All serious adverse events (SAEs) meeting criteria for expedited reporting to the US FDA will be reported to the FDA and all IRBs in accordance with regulatory timelines.
7. The sponsor's study safety representative *and* a separate independent medically qualified and clinical trials-experienced safety monitor physician will monitor aggregate study level safety and tolerability on a recurring basis: The first review will occur after approximately 25% of the projected sample size of subjects have completed the EOS Visit and the second review will occur after approximately 50% of the projected sample size of subjects have completed the EOS Visit. These reviews will be based on blinded, select listings and summary tables of the evolving safety and tolerability data for each arm of the study. The sponsor's study safety representative and the independent safety monitor physician will review the blinded study data to determine if there is a sufficiently clinically significant difference between the blinded treatment arms in terms of frequency, severity, and/or seriousness of adverse events to take actions such as 1) unblinding specific safety data; 2) eliminating one or more of the planned dose up-titrations (e.g., not escalating from 8 to 10 mg BID); or 3) suspending new enrollment in the study until further safety review and consultation with the PI's and sub-I's can be performed. Decision-making will depend on the specifics of the safety and tolerability data reviewed. If the sponsor's study safety representative and/or the independent safety monitor physician decide that any data should be unblinded, then the unblinded data will be reviewed only by the independent safety monitor physician.

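### Does giving the sponsor's study safety representative masked safety output split by arm breach the sponsor's blind?

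*Protocol*

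**What the plan says.** Item 7 of Section 10.4 (Safety Monitoring and Risk Mitigation Plan) sets two aggregate safety reviews, after roughly 25% and 50% of the projected sample have completed the End of Study visit. Both the sponsor's study safety representative and the independent safety monitor physician receive "blinded, select listings and summary tables of the evolving safety and tolerability data for each arm of the study". Their task is "to determine if there is a sufficiently clinically significant difference between the blinded treatment arms" in the frequency, severity or seriousness of adverse events. They may then unblind specific safety data, drop a planned up-titration step or suspend enrolment. If either of them decides to unblind, "then the unblinded data will be reviewed only by the independent safety monitor physician".

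Section 4.8 (Study Blinding) sets the standard: "the treatment assignment and drug contents are not revealed to the sponsor". After an emergency unblinding at a site, the sponsor's "study safety representative, and any other investigators, must not be informed of the treatment assignment". After an accidental unblinding, the "investigator will not reveal the identity of the study treatment" to the representative, other sponsor staff or the contract research organisation.

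The representative also has a part in running the trial. When compliance is below 75% or above 125%, the subject's "continued participation in the study should be discussed with the study safety representative" (Section 4.4). Sections 7.2.3 and 7.2.4 call for the same consultation on up-titration when compliance is below 75%, and Section 10.1.11 calls for it on continued participation after visual hallucinations.

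**The concern.** The two sections seem to pull against each other. Section 4.8 takes care that nobody tells the representative an assignment, while item 7 gives the same role output separated by arm and asks for a comparison. In a two-arm trial, an excess of events on one side points to the active drug. The rules in Section 4.8 govern disclosure; none of them governs inference. If the listings carried an arm code, a confident inference about the columns would become knowledge of each listed subject's treatment. The representative could then bring that knowledge to decisions on up-titration, continued participation or, under item 8 of Section 10.4, re-opening or stopping the trial after a death. At stake would be the sponsor-side blind and, through it, the even-handed conduct of the trial.

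**Working it through.** **Inputs from the protocol.** About 106 subjects (Section 6.1; 53 per group, Section 11.3), randomised 1:1 (Section 4.7). The first review comes at 0.25 × 106 = 26.5 subjects, about 13 per arm. The second comes at 0.50 × 106 = 53 subjects, about 26 per arm. Adverse-event rates are redacted in Section 1.4.3, so all rates below are assumptions, with placebo held at 20%.

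**How well could a masked arm be guessed?** Let A and P be the numbers of subjects with an event in the active and placebo arms, both binomial. The probability that the arm with more events is the active one, with ties split evenly, is

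P(A > P) + ½ · P(A = P).

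For 40% versus 20%: at 13 per arm, 0.823 + ½ × 0.090 = 0.868; at 26 per arm, 0.927 + ½ × 0.034 = 0.944.

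A stricter measure takes a reader who does not know the rates and believes only that the active arm has the higher one. With independent uniform priors on the two rates, the reader's probability that a given arm is active is the posterior probability that its rate is the higher. The last two columns show how often that probability reaches 95% for the right arm and for the wrong arm.

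| Active vs placebo | Guess correct (13 / 26 per arm) | ≥95% certain and right (13 / 26) | ≥95% certain and wrong (13 / 26) |
|---|---|---|---|
| 20% vs 20% | 50% / 50% | 4.7% / 4.8% | 4.7% / 4.8% |
| 25% vs 20% | 62% / 67% | 8.2% / 11.1% | 2.4% / 1.9% |
| 30% vs 20% | 72% / 80% | 12.7% / 20.8% | 1.1% / 0.7% |
| 40% vs 20% | 87% / 94% | 25.8% / 48.2% | 0.2% / 0.1% |
| 50% vs 20% | 95% / 99% | 43.9% / 75.9% | 0.0% / 0.0% |

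Strong identification needs a doubling of the event rate or more. At a five-point difference the reader is seldom sure; at equal rates the reader is wrongly sure as often as rightly.

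**Whose treatment could still be influenced?** The reviews are triggered by subjects who have completed the End of Study visit at Day 35, a week after the last dose at Day 28 (Sections 7.2.5 and 7.2.6). Dosing is over for them. Subjects still on treatment matter only if the output also covers ongoing subjects, which item 7 does not say. Assuming that it does, and that 106 subjects are recruited evenly, the expected number within their 28 days is 106 × 28 / (recruitment days). For 6 months (about 182.6 days) that is 16.3; for 24 months (about 730.5 days) it is 4.1. The number before Day 15, when the last up-titration falls due, is half of that: 8.1 and 2.0. The recruitment period is an assumption.

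**What would have to be true for the result to be biased?**

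1. Event rates differ enough for the guess to be good (unknown).
2. The listings are grouped or coded by arm. Item 7 says only that the data are for each arm. If just the summary tables are split, the inference stops at two columns and identifies nobody.
3. The output includes subjects still on treatment (not stated).
4. One of those subjects meets a consultation trigger: compliance outside 75% to 125%, or visual hallucinations. For low compliance, Section 6.4 already lists "Subject is not at least 75% compliant with study drug administration at any study visit" as a ground for discontinuing treatment.
5. The effect reaches the endpoint. Section 8.1.1 has a blinded central rater supply the scores used in the efficacy analysis, and the protocol gives the representative no part in rating or analysis.

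**Is there a contradiction?** Section 4.8 forbids revealing the assignment. Item 7 supplies masked data and routes unmasked data to the independent physician alone. Both instructions can be followed at once.

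**The case for a change.** The best argument for the concern is that the exposure grows with exactly the imbalance the review exists to find: if the arms differ enough to matter, the representative probably knows which is which. The protocol is also stricter elsewhere. For the blinded variance estimate in Section 11.5.4, a non-study statistician does the work, and the sponsor sees neither the randomisation schedule nor the data. A figure title in the protocol's list of figures links central nervous system events to drug exposure, and Section 11 sorts study listings by treatment group by default, so coded listings are plausible. A remedy is available too: arm-split output to the independent physician only, pooled output to the representative.

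It stands that arm-separated masked output carries some information, and a sponsor could reasonably prefer the tighter arrangement. The rest is weaker. The figure title gives no rates. The default sort order is not stated to apply to these interim outputs. Section 3.1 does name Group A and Group B, but nothing says the masked tables carry those labels.

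The remedy also has a price. Pooled tables cannot show a difference between arms, which is the purpose of item 7. The representative could still ask for unblinded review, but without sight of the imbalance that would prompt the request. One person would make the only between-arm safety comparison until a data monitoring committee that is optional, comes at about 75% of planned subjects and is convened to review efficacy (Section 11.5.4).

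**Conclusion.** The concern does not hold. Item 7 deliberately has two medical readers compare masked arms and reserves formally unblinded data for the independent one. That is compatible with Section 4.8. The residual risk to the blind cannot be sized from the protocol, because the event rates are redacted. On the assumed rates, a reader who does not know them would be rightly at least 95% certain between about 5% of the time (equal rates, and wrongly certain as often) and 76% of the time (50% versus 20%, second review). Even a confident guess has little to act on. The triggering subjects have finished treatment, the consultation triggers are narrow, arm coding of the listings is not stated, and a blinded central rater scores the primary endpoint. Whether a second between-arm safety reader is worth this exposure is a trade-off on which experienced statisticians differ. The protocol has chosen one defensible side of it, and no correction is needed.

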11 STATISTICAL METHODS

Descriptive statistical methods will be used to summarize the data from this study, with statistical testing performed for the efficacy endpoints. All statistical testing will be two-sided and will be performed using a significance (alpha) level of 0.05. Unless stated otherwise, the term "descriptive statistics" refers to number of subjects (n), mean, median, standard deviation, minimum and maximum for continuous data, and frequencies and percentages for categorical data. Presentations of data will be summarized by treatment group and overall. The term "treatment group" refers to the following: Placebo or CX-8998. All available data for enrolled subjects will be listed in by subject listings. Unless otherwise noted, the data will be sorted first by treatment group, subject number, and then by date within each subject number.

All statistical analyses will be conducted with the SAS® System, version 9.4 or higher.

11.1 Statistical Analysis Plans

A SAP will be created and approved prior to the unblinding of the study data. This document will provide a more technical and detailed description of the proposed data analysis methods and procedures.

11.2 Study Hypothesis

The primary statistical hypothesis for the study is provided below.

- $H_{02}: \mu_{\text{Placebo}} = \mu_{\text{CX-8998}}$, i.e., there is no difference between treatment groups in the mean change from Baseline in TETRAS performance scale at end of treatment
- $H_{12}: \mu_{\text{Placebo}} \neq \mu_{\text{CX-8998}}$, i.e., there is a difference between treatment groups in mean change from Baseline in TETRAS performance scale at end of treatment

11.3 Determination of Sample Size

Subjects will be randomized to one of two treatment groups: Placebo or CX-8998. Based on similarly designed studies, a sample size of approximately 106 subjects should be sufficient to provide preliminary safety and efficacy information on CX-8998 when administered according to this protocol.

A sample size of 53 subjects per group has at least 90% power to detect at least a 5.5-point difference between CX-8998 and placebo in change from Baseline to Day 28 in the TETRAS performance subscale when the standard deviation is 7.5 and alpha=0.05 (PASS 2008: Two sample t-test – Normal Non-Parametric Adjustment) and to account for dropouts and subjects who are excluded because of major protocol deviations.

A blinded interim analysis of variance will be conducted once 50% of subjects have been enrolled and followed for 28 days or discontinued from the study. Based on the results of this analysis, the sample size may be modified to achieve the desired power for the study.

11.4 Analysis Populations

The populations defined for analysis will include the intent-to-treat (ITT) population, safety population, and a pharmacokinetic population. Additional analysis populations may be defined to evaluate study results. Any additional analysis populations will be defined in the SAP.

- **Intent-To-Treat Population:** The ITT population will include all subjects who are randomized. The ITT population will be used for analyses of accountability, demographics, and efficacy. Subjects will be analyzed according to the treatment as randomized.
- **Safety Population:** The safety population will include all subjects who are randomized and receive at least one dose of randomized treatment. Subjects who receive treatment other than that intended will be analyzed according to the treatment received. The safety population will be the primary population for all analyses of safety data.
- **PK Population:** The PK population will consist of all subjects for whom PK samples were obtained, received study treatment, and for whom sufficient plasma concentrations are available.

11.5 Data Analysis

11.5.1 Efficacy Analyses

11.5.1.1 Primary Efficacy Analyses

The primary efficacy analysis of the TETRAS performance subscale (as scored by the central rater) will be conducted using an analysis of covariance (ANCOVA) model with fixed effects for treatment, concomitant anti-tremor medication use, site type, and Baseline value of the TETRAS performance subscale. The primary hypothesis to be tested will be if the mean change from Baseline in TETRAS performance scale indicates that the CX-8998 arm is different from placebo. All testing will be performed using the least square (LS) means from the ANCOVA model and a two-sided test at the alpha=0.05 level of significance. If the data indicate a departure from the normal distribution, a corresponding rank test will be performed.

11.5.1.2 Secondary and Exploratory Efficacy Analyses

Analyses of the continuous secondary and exploratory endpoints will be conducted using the same type of ANCOVA model as described for the primary endpoint, with baseline values included only as applicable. All secondary and exploratory analyses will be conducted using two-sided tests at the alpha=0.05 level of significance. Analysis of findings from the neurophysiology substudy will be presented in a separate study report.

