3.3 Endpoints

3.3.1 Primary Endpoint

The change from Baseline to Day 28 on the TETRAS Performance subscale, as scored by the central rater

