3.3.2 Secondary Endpoints

1. Change from Baseline to Day 28 on the TETRAS Activity of Daily Living subscale
2. Change from Baseline to Day 28 in accelerometry score, as measured by Kinesia ONE
3. Safety and tolerability endpoints:
 - a. adverse events,
 - b. changes from baseline in QTcF and other ECG parameters,
 - c. clinical safety laboratory assessments (clinical chemistry, hematology, and urinalysis),
 - d. C-SSRS
 - e. Epworth Sleepiness Scale (ESS),
 - f. vital signs,
 - g. number (%) of subjects who did not complete the study,
 - h. number (%) of subjects who did not complete the study due to adverse events.

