3.3.3 Exploratory Endpoints

1. Change from Baseline on the Total TETRAS score to Day 15 and Day 28, as scored by the central rater.
2. Change from Baseline to Day 15 on the TETRAS Performance subscale, as scored by the central rater.
3. Change from Baseline to Day 15 in accelerometry score as measured by Kinesia ONE
4. Change from Baseline to Day 15 and Day 28 in Kinesia ONE amplitude measures
5. Treatment success at the end of therapy as measured by Patient Global Impression of Change (PGIC)
6. Treatment success at the end of therapy as measured by Clinical Global Impression of Improvement (CGI-I)
7. Treatment success at the end of therapy as measured by Goal Attainment Scaling (GAS)

8. Change from Baseline in Quality of Life in Essential Tremor Questionnaire (QUEST)
9. Digital biomarkers will be explored in tremor populations of up to 50 subjects using a battery of optional clinical outcomes and digital biomarkers (details will be provided in relevant substudy addendums).

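### Section 11.5.1.2 tests both secondary efficacy endpoints and every exploratory endpoint at full two-sided 0.05, with no testing order, no link to the primary result and no statement that these p-values are nominal

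*Protocol*

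**What the plan says.** All references are to the current version of the protocol, the one with about 106 subjects. Section 3.3.1 names one primary endpoint: "The change from Baseline to Day 28 on the TETRAS Performance subscale, as scored by the central rater". Section 11.5.1.1 tests it with "a two-sided test at the alpha=0.05 level of significance".

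Section 3.3.2 lists two secondary efficacy endpoints, "Change from Baseline to Day 28 on the TETRAS Activity of Daily Living subscale" and "Change from Baseline to Day 28 in accelerometry score, as measured by Kinesia ONE"; its third item is safety and tolerability. Section 3.3.3 lists the exploratory endpoints, starting with "Change from Baseline on the Total TETRAS score to Day 15 and Day 28, as scored by the central rater" and "Change from Baseline to Day 15 on the TETRAS Performance subscale, as scored by the central rater".

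Section 11.5.1.2 gives the testing rule for the last two groups: "All secondary and exploratory analyses will be conducted using two-sided tests at the alpha=0.05 level of significance". The synopsis carries the same sentence under the secondary efficacy analyses. Section 11 is broader: "All statistical testing will be two-sided and will be performed using a significance (alpha) level of 0.05".

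None of these places sets an order among the secondaries, makes them depend on the primary result, splits alpha, or says that the non-primary p-values are descriptive.

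**The concern.** The sentence is a stated rule, since it gives each secondary and exploratory test its own full level of significance. Someone who follows the text after a missed primary may still report ADL or accelerometry as significant at 0.05. With two such chances, the probability that at least one arises from noise exceeds 5%.

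The two measures matter because they answer the first two secondary objectives in Section 2.2, daily activities and objective quantification of tremor. A significant result on either would shape what the trial is taken to show about efficacy.

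**Working it through.** **Plan's own figures.** The protocol states no family-wise error rate, so there is none to reproduce. Its sizing (Section 11.3) concerns the primary test alone: 5.5 points, SD 7.5, two-sided 0.05, at least 90% power. The normal formula gives n = 2 × (1.960 + 1.282)² × 7.5² / 5.5² = 39.1, so 40 per group. The t-test needs 41, and 41 × π/3 = 42.9, so 43 with the non-parametric adjustment. At 53 per group the adjusted power is 95.5%, so the statement reproduces. It says nothing about the secondaries.

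**Inputs.** Level 0.05, two-sided, for each test (Sections 11, 11.5.1.1 and 11.5.1.2); one primary test (3.3.1); two secondary efficacy tests (3.3.2). The correlation between test statistics is not given, so a common value ρ from 0 to 0.9 is assumed.

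**Formulas, all null hypotheses true.**

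1. Independent tests: P(at least one of m) = 1 − 0.95^m. For m = 2 this is 1 − 0.9025 = 9.75%. For m = 3 it is 1 − 0.857375 = 14.26%.
2. Equicorrelated normal statistics with c = 1.96: P = 1 − ∫ φ(t) [Φ((c − √ρ t)/√(1−ρ)) − Φ((−c − √ρ t)/√(1−ρ))]^m dt.
3. Missed primary with at least one significant secondary: P(any of the three) − P(primary significant) = P(any of the three) − 5%.

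| ρ | Any false-positive secondary (m = 2) | Any among primary and secondaries (m = 3) | Missed primary, significant secondary |
|---|---|---|---|
| 0 | 9.75% | 14.26% | 9.26% |
| 0.3 | 9.51% | 13.62% | 8.62% |
| 0.5 | 9.07% | 12.54% | 7.54% |
| 0.7 | 8.35% | 10.92% | 5.92% |
| 0.8 | 7.81% | 9.82% | 4.82% |
| 0.9 | 7.04% | 8.36% | 3.36% |

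**Where in the range.** Section 8.1 describes ADL and Performance scores as highly correlated and upper-limb ratings as strongly related to accelerometry. That concerns scores rather than changes from baseline, but it is the only evidence in the protocol. It points to higher correlation, and so to the lower rows.

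**With a fixed sequence.** Under the global null, a false positive can occur only if the primary is first significant, so the rate over the three tests is 5%. Simulation with 2,000,000 draws gives 5.00% at ρ = 0 and at ρ = 0.5, against 14.3% and 12.6% without the sequence.

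**The case against.** The strongest reply is that Section 11.5.1.2 fixes only sidedness and a level per test. It does not say in so many words that the secondaries count whatever the primary shows. Section 11.1 leaves technical detail to the SAP, which was not available here, and a fixed sequence there would also use 0.05 at each step. This stands in part: such a sequence could sit beside the protocol sentence for the two secondaries. But the sentence as written already assigns every secondary and exploratory test a level of significance, and Section 11 reinforces it. A reader of the protocol alone has no ground for treating any of these results as conditional or nominal.

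The second reply is that this is a Phase 2 trial seeking preliminary information, with one primary hypothesis and sizing on that endpoint alone. This is a good reason to call the other p-values supportive, but the protocol does not do so.

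Three stronger readings are tempting and are not supported:

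- A reader might infer that the secondaries have the same standing as the primary, or that the primary error rate is inflated. The protocol ranks its endpoints, and the primary test keeps its own 5% as far as this rule goes.
- A reader might pool the ten or more exploratory tests with the secondaries and quote one large error rate. Over twelve non-primary tests that rate runs from about 13% to 46% as ρ goes from 0.9 to 0. The exploratory endpoints are declared as such, overlap heavily and are no confirmatory family, so no pooled rate is claimed.
- A reader might take the ρ = 0.5 values as properties of the plan. They rest on an assumption that the protocol does not supply.

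Finally, a fixed sequence is not the only valid choice. Holm between the two secondaries after a significant primary, or calling both nominal, would also close the gap.

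**Conclusion.** The concern holds for the two secondary efficacy endpoints. Even at a correlation of 0.9, the chance of at least one false-positive secondary (7.0%) and of any false positive among the three tests (8.4%) exceeds 5%. The practical risk is a missed primary followed by a claimed secondary: about 3 to 9% when the drug has no effect on any of the three. These figures assume the global null and equal correlation among the three statistics. The point warrants a change because the present rule permits a claim that the design does not protect, and a better rule costs almost nothing. It does not undermine the primary analysis.

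**What to change.** Replace the sentence in Section 11.5.1.2 and in the synopsis with a rule to this effect:

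> If the primary test is significant at two-sided 0.05, the secondary efficacy endpoints are tested in the order of Section 3.3.2 (TETRAS ADL at Day 28, then Kinesia ONE score at Day 28), each at two-sided 0.05, stopping at the first non-significant result. All other p-values, including those for secondaries after the sequence stops and for all exploratory endpoints, are nominal and support no claim of statistical significance.

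Align Section 11 so that the 0.05 significance level applies only to the tests in this sequence, and carry the same statement in the SAP before unblinding.

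The order matters as well as the condition on the primary. If the drug moved the primary but neither secondary, testing both at 0.05 once the primary is significant would still leave two chances of a false claim; the sequence leaves one. It holds the error over the three tests at the level of the primary test. That level is 5% provided the optional unblinded efficacy review in Section 11.5.4 does not itself inflate it.

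No subjects, assessments or primary power are lost, and every estimate, interval and p-value is still reported. The cost is that a secondary result after a missed primary, or a Kinesia ONE result after a non-significant ADL test, can only be called nominal.
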